8.8. Biomarkers

Biomarkers (specified analyses) are not evaluated in this study.

8.8.1. Specified Gene Expression (RNA) Research

Specified gene expression (RNA) research is not included in this study.

8.8.2. Specified Protein Research

Specified protein research is not included in this study.

8.8.3. Specified Metabolomic Research

Specified metabolomic research is not included in this study.

8.8.4. Banked Biospecimens for Biomarkers

A 4 mL blood sample optimized for biomarkers (**Prep B2.5**) will be collected and isolate serum retained as local regulations and IRBs/IECs allow.

A 2.5 mL blood sample optimized for RNA isolation (Prep R1) will be collected as local regulations and IRBs/IECs allow.

Banked Biospecimens may be used for research related to the study intervention and AD. Genes and other analytes (eg, proteins, RNA, non-drug metabolites) may be studied using the banked samples.

Unless prohibited by local regulations or IRB/EC decision, participants will be asked to indicate on the consent form whether they will allow their banked samples to also be used to design and conduct research in order to gain a further understanding of other diseases and to advance science, including development of other medicines for patients. This component of the sampling banking is optional for participants; they may still participate in the study even if they do not agree to the additional research on their banked samples. The optional additional research does not require the collection of any further samples.

Refer to [Appendix 5](#) for information regarding genetic research. Details on processes for collection and shipment of these samples can be found in the study manual.

8.9. Medical Resource Utilization and Health Economics

Health economics/medical resource utilization and health economics parameters are not evaluated in this study with the exception of self-reported healthcare resource utilization as indicated in the [Schedule of Activities](#).

9. STATISTICAL CONSIDERATIONS

9.1. Estimands and Statistical Hypotheses

9.1.1. Estimands

There are two estimands for the study.

Estimand 1, composite estimand:

- Population: Participants with moderate-to-severe Atopic Dermatitis (AD) as defined by the inclusion criteria to reflect the targeted participant population;
- Variable: response based on achieving at least a 4-point improvement in the severity of PP-NRS from baseline (PP-NRS4) at Week 2; for participants who drop out for any reason or use rescue therapy (Section 6.5.2) at any time during the treatment period, the response will be defined as “non-responsive” after that point;

- Interventional effect: Effect of randomized treatment accounting for treatment adherence, rescue therapy, and response; the intercurrent event (drop-out or use of rescue therapy) is captured through the variable definition;
- Population-level summary: differences in proportions of responders between abrocitinib and dupilumab.

Estimand 1 composite estimand is the primary estimand for the primary and key secondary endpoints: PP-NRS4 response at Week 2, EASI-90 at Week 4, and EASI-90 at Week 16. Other binary outcome measures such as response based on PP-NRS4 and EASI-90 at all other scheduled timepoints, EASI-75, and IGA will follow the same structure.

Estimand 2, hypothetical estimand:

- Population: Participants with moderate-to-severe Atopic Dermatitis (AD) as defined by the inclusion criteria to reflect the targeted participant population;
- Variable: Percent change from baseline in SCORAD at all scheduled timepoints;
- Interventional effect: Effect of randomized treatment as if all participants maintain their randomized treatment; drop-out for any reason and use of rescue therapy are the intercurrent events; data after dropout or use of rescue therapy at any time during the treatment period will be censored;
- Population-level summary: Difference in least-square means between abrocitinib and dupilumab.
- Percent change from baseline or change from baseline to each specific post baseline scheduled time points in a continuous outcome measure such as HADS, POEM, DLQI, and EQ-5D-5L will follow the same structure as defined for SCORAD.

9.2. Sample Size Determination

This is a randomized, double-blind, double-dummy, active-controlled, multi-center study to assess the efficacy and safety of abrocitinib 200 mg QD compared with dupilumab (as per label guidelines) in adult participants on background topical therapy, with moderate to severe AD. The treatment duration is 26 weeks. A total of approximately 600 participants will be enrolled from approximately 220 sites globally. There are primary efficacy assessments at Week 2 and Week 4, and a key secondary efficacy assessment at Week 16. Efficacy and safety endpoints will be assessed throughout the entire study.

A total sample of 600 participants, with 300 participants randomized to abrocitinib, 300 participants randomized to dupilumab (1:1 randomization) is planned. The proposed sample size provides adequate power for all superiority hypotheses, as follows:

Week 2: This sample size would provide at least 99% power to detect a difference assuming a difference of at least 25% in PP-NRS4 between abrocitinib and dupilumab and assuming the dupilumab response rate is 11% at Week 2.

Week 4: This sample size will provide approximately 99% power to detect a difference assuming a difference of at least 15% in Week 4 EASI-90 between abrocitinib and dupilumab and assuming the dupilumab response rate is 12%.

Week 16: this sample size will provide at least 99% power to show the difference is no more than 10% favoring dupilumab in EASI-90 at Week 16 (non-inferiority (NI) with a 10% margin), assuming the abrocitinib response rate is 53% and the dupilumab response rate is 43% at Week 16. This sample size will also provide approximately 70% power to demonstrate superiority of abrocitinib 200 mg QD to dupilumab as measured by EASI-90 response at Week 16.

While the power to detect a difference at the early time points of 2 and 4 weeks and non-inferiority at week 16 is strong implying a decrease sample size could be used, the power to demonstrate superiority at week 16 requires the larger number of participants. Superiority at week 16 is a valuable endpoint for the scientific community and prescribers justifying the larger sample size. In addition, the study design avoids exposing participants to the use of placebo alone. While a larger number of participants are utilized, they will be guaranteed treatment on 1 of the 2 active treatment arms, which allows for potential benefit for all participants included in the study.

The 10% NI margin between abrocitinib and dupilumab was chosen for Week 16 EASI-90 based on the historical data from dupilumab in treating participants with moderate to severe atopic dermatitis described in [Section 2.2.2](#). Difference and the associated 95% confidence intervals (CIs) between dupilumab and placebo in combination therapy was 31.2% (22.9, 39.5). The 10% NI margin preserves around two thirds of the treatment effect of dupilumab. Added advantages of convenient route of administration, early onset of pruritus relief, and unlikely development of anti-drug antibodies support that a <10% difference would not be considered clinically important.

In projecting the difference between abrocitinib and dupilumab in Week 16 EASI-90 in combination therapy, the following assumptions were made. Based on the monotherapy and combination therapy studies in the dupilumab program ([Section 2.2.2](#)), and the monotherapy studies in the abrocitinib program ([Section 2.2.3](#)), the projected difference between abrocitinib in combination with TCS and dupilumab in combination with TCS will be similar to the projected difference between abrocitinib and dupilumab under the monotherapy setting. Similar assumptions were made for Week 2 PP-NRS4 response and Week 4 EASI-90.

The familywise Type I error rate (for testing the primary and key secondary endpoints) will be strongly controlled at 5% (2-sided) using a sequential multiple testing procedure outlined in [Section 9.4.2](#).

9.3. Populations for Analyses

For purposes of analysis, the following populations are defined:

Population	Description
Enrolled	All participants who sign the ICD.
Randomly Assigned to Study Intervention	All participants who were randomly assigned to abrocitinib or dupilumab.
Full Analysis Set (FAS)	All randomized participants receiving at least one dose of study intervention. Participants will be analyzed according to the intervention to which they were randomized.
Per-Protocol Analysis Set (PPAS)	
All randomized participants receiving at least one dose of study intervention who had no major protocol violations.
 
This set will include participants who:
 
 • Were eligible for the study by way of meeting key inclusion criteria and none of the key exclusion criteria. • Had valid and non-missing baseline efficacy data (EASI score). • Had actual, observed EASI scores at Week 16. • Took the correct randomized treatment for at least 80% and at most 120% of the assigned amount until Week 16. • Had no other major protocol violations as determined by the clinical team prior to database lock. A major protocol violation in this context is one that is likely to affect materially the efficacy responses of the participant and will be defined by the clinical team before database is locked and any analysis is performed for this study.
Safety	All participants randomly assigned to study intervention and who take at least 1 dose of study intervention. Participants will be analyzed according to the intervention they actually received.

Unless otherwise specified, all observations after dropout or use of rescue therapy will be censored. For the responder analysis, data after dropout or use of rescue therapy will be defined as “non-responsive” after that point.

9.4. Statistical Analyses

Detailed methodology for summary and statistical analyses of the data collected in this study is outlined here and further detailed in a statistical analysis plan (SAP), which will be maintained by the sponsor. The SAP may modify what is outlined in the protocol where appropriate; however, any major modifications of the primary or key secondary endpoint definitions or their analyses will also be reflected in a protocol amendment.

The SAP will be developed and finalized before database lock and will describe the participant populations to be included in the analyses, and procedures for accounting for missing, unused, and spurious data. This section is a summary of the planned statistical analyses of the primary and secondary endpoints.

9.4.1. Efficacy Analyses

Endpoint	Statistical Analysis Methods
Primary	
 
• The primary endpoints (PP-NRS4 response at Week 2, and EASI-90 at Week 4) will be analyzed using the Cochran Mantel Haenszel (CMH) test adjusted by baseline disease severity group (moderate and severe). The difference between the abrocitinib 200 mg group and the dupilumab 300 mg group in the proportion of participants achieving the response along with its 95% confidence interval (using the normal approximation for the difference in binomial proportions) will be reported. The difference in proportions will be calculated within each randomization stratum. The final estimate of the difference in proportions will be a weighted average of these stratum specific estimates using CMH weights. This analysis is based on Estimand 1 composite estimand and on population defined set FAS. 
• Secondary analysis 1: CMH test on population defined set FAS. This analysis will not consider the use of rescue therapy as an intercurrent event. For participants who drop out for any reason, the response will be defined as “non-responsive” after that point. 
• Secondary analysis 2 utilizes the longitudinal nature of the binary endpoint. A Generalized Linear Mixed Model (GLMM) will be fit to all observed data (ie, regardless of rescue therapy and without defining missing data as “non-response”). Under the missing at random (MAR) framework, imputations will be based on the posterior predictive probability of response obtained from the posterior distribution under the mixed model. For each such completed dataset, the estimates of the proportions and CMH-

Endpoint	Statistical Analysis Methods
	
weighted difference of proportions between abrocitinib and dupilumab will be obtained and Rubin’s rule will be used to combine the multiple estimates and standard errors across the imputed datasets and provide p-values.

Key Secondary	
 • The non-inferiority test of the key secondary endpoint EASI-90 at Week 16 will be analyzed using the 95% CMH weighted confidence interval adjusted by baseline disease severity group (moderate and severe). NI will be declared if the lower bound of the confidence interval for the response difference (abrocitinib - dupilumab) is greater than -10%. This analysis is based on Estimand 1 composite estimand and on population defined set FAS. • For the superiority test of the key secondary endpoint EASI-90 at Week 16 will be analyzed using the Cochran Mantel Haenszel test adjusted by baseline disease severity group (moderate and severe) similarly to the primary endpoints. This analysis is based on Estimand 1 composite estimand and on population defined set FAS. • Secondary analysis 1: CMH test on population defined set PPAS. • Secondary analysis 2: CMH test on population defined set FAS. This analysis will not consider the use of rescue therapy as an intercurrent event. For participants who drop out for any reason, the response will be defined as “non-responsive” after that point. • Secondary analysis 3: Missing observations will be multiply imputed similarly to secondary analysis 2 of the primary endpoints.
Secondary	
 • The secondary endpoints which are summarized as proportions such as EASI-90 at Week 12, will be analyzed using the same method as for the primary endpoints. This would also apply to any other binary endpoint in the study, such as the proportion of response based on IGA of clear (0) or almost clear (1) and ≥ 2-point improvement from baseline. • For continuous endpoints, a mixed effect model with repeated measures (MMRM) will be used. This model will include the factors (fixed effects) for treatment group, disease severity group, visit, treatment by visit interaction, and relevant baseline value. Within the framework of MMRM, the treatment difference will

Endpoint	Statistical Analysis Methods
	be tested at Week 16, as well as at the other time points by time point specific contrasts from the MMRM model. This analysis is based on Estimand 2 hypothetical estimand and on population defined set FAS. Observations after dropout or use of rescue therapy will be censored.
Exploratory	Will be described in the statistical analysis plan finalized before database lock.

9.4.2. Type I Error Control Procedure

The Type I error rate is set at 5% (two sided). The familywise Type I error rate (for testing the primary and key secondary endpoints) will be strongly controlled at 5% using a sequential testing approach.

The procedure will test all hypothesis sequentially. If one hypothesis is not rejected at the 5% level, then the statistical significance will be not claimed for the subsequent hypotheses testing. The procedure will first test superiority of PP-NRS4 response at Week 2 and then EASI-90 at Week 4 between abrocitinib and dupilumab by CMH test specified in the primary analysis. If both hypotheses are rejected, the procedure will continue to test the NI of EASI-90 at Week 16 between abrocitinib and dupilumab. The 95% CMH weighted confidence interval will be constructed for the response difference and NI will be declared if the lower bound of the confidence interval for the response difference (abrocitinib - dupilumab) is greater than -10%. If the non-inferiority is achieved, the procedure will continue to test superiority of EASI-90 at Week 16 between abrocitinib and dupilumab by CMH test specified in the analysis for the key secondary endpoint.

A sequential, step-down approach with the PP-NRS4 endpoint from Week 2 to earlier time points will be utilized as an additional family of hypothesis tests once statistical significance is demonstrated at Week 2. Specifically, further hypotheses of no difference in PP-NRS4 between abrocitinib and dupilumab will be assessed at Day 15, Day 14, Day 13, Day 12, ..., Day 2, in that order. Any hypotheses after the last Day for which the comparison is significant will not be considered statistically significant. All hypotheses in the sequence will be assessed at the 5% level of significance. Although this will not protect the Type-I error for the family of all possible comparisons, it will provide Type-I error protection for the family of PP-NRS4 comparisons over the first 2 weeks.

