5. GENERAL METHODOLOGY AND CONVENTIONS

5.1. Hypotheses and Decision Rules

The Type I error rate is set at 5% (two sided). The familywise Type I error rate (for testing the primary and key secondary endpoints) will be strongly controlled at 5% using a sequential testing approach.

The procedure will test all hypothesis sequentially. If one hypothesis is not rejected at the 5% level, then the statistical significance will be not claimed for the subsequent hypotheses testing. The procedure will first test superiority of PP-NRS4 response at Week 2 and then EASI-90 at Week 4 between abrocitinib and dupilumab by CMH test specified in the primary analysis. If both hypotheses are rejected, the procedure will continue to test the NI of EASI-90 at Week 16 between abrocitinib and dupilumab. The 95% CMH weighted confidence interval will be constructed for the response difference and NI will be declared if the lower bound of the confidence interval for the response difference (abrocitinib - dupilumab) is greater than -10%. If the non-inferiority is achieved, the procedure will continue to test superiority of EASI-90 at Week 16 between abrocitinib and dupilumab by CMH test specified in the analysis for the key secondary endpoint.

The following figure illustrates the procedure showing the sequence of the tests.

A sequential, step-down approach with the PP-NRS4 endpoint from Week 2 to earlier time points will be utilized as an additional family of hypothesis tests once statistical significance is demonstrated at Week 2. Specifically, further hypotheses of no difference in PP-NRS4 between abrocitinib and dupilumab will be assessed at Day 15, Day 14, Day 13, Day 12, ..., Day 2, in that order. Any hypotheses after the last Day for which the comparison is significant will not be considered statistically significant. All hypotheses in the sequence will be assessed at the 5% level of significance. Although this will not protect the Type-I error for the family of all possible comparisons, it will provide Type-I error protection for the family of PP-NRS4 comparisons over the first 2 weeks.

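### The stopping sentence for the daily PP-NRS4 step-down (Day 15 to Day 2) is empty if applied literally, so it does not state the stop-at-first-failure rule that the claimed error protection needs

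*Protocol*

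**What the plan says.** Protocol 9.4.2 and SAP 5.1 carry the same text on this point. It has two parts.

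- **Main sequence.** The primary and key secondary hypotheses are tested in a fixed order, with an explicit stop rule: "If one hypothesis is not rejected at the 5% level, then the statistical significance will be not claimed for the subsequent hypotheses testing".
- **Daily itch family.** A later paragraph introduces "A sequential, step-down approach with the PP-NRS4 endpoint from Week 2 to earlier time points", which "will be utilized as an additional family of hypothesis tests once statistical significance is demonstrated at Week 2". The hypotheses "will be assessed at Day 15, Day 14, Day 13, Day 12, ..., Day 2, in that order". On level: "All hypotheses in the sequence will be assessed at the 5% level of significance". On stopping: "Any hypotheses after the last Day for which the comparison is significant will not be considered statistically significant".

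The paragraph disclaims protection over all possible comparisons but says that "it will provide Type-I error protection for the family of PP-NRS4 comparisons over the first 2 weeks".

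Three other places give the rule practical force. SAP 5.2 (General Methods) allows no claim of statistical significance unless Section 5.1 or Section 6 notes an exception, so SAP 5.1 is what licenses the daily claims. SAP 6.2.2.1 produces a CMH p-value for each of Days 2 to 15. SAP Appendix 2 bases those tests on the value from the actual diary day.

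**The concern.** A fixed-sequence procedure with every test at 5% keeps the familywise error at 5% only if it stops at the first non-significant result. The sentence written for this family refers instead to the last significant day. In testing order, whatever follows the last significant day has already failed, so the sentence removes no claim.

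Take a case where Days 15 to 9 are significant, Days 8 to 4 are not, Day 3 has p<0.05 and Day 2 does not. Read literally, Day 3 is the last significant day and stands as a claim. Under stop-at-first-failure, the earliest claimable day is Day 9.

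Broken runs like this are plausible. The tests use single-day diary values, and under SAP 5.3.1 (Method 1) intermittently missing values stay missing, so the denominator can change from day to day.

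What is at stake is the earliest day on which an itch difference may be claimed. Protocol 2.2.3 presents rapid itch relief as a distinguishing feature of the drug class, and Protocol 9.2 cites early itch relief in support of the non-inferiority margin. The onset day is therefore likely to be reported prominently, and the plan attaches an error-control statement to it.

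**Working it through.** **Inputs from the documents**

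- Level: "The Type I error rate is set at 5% (two sided"), and 5% for each daily test (Protocol 9.4.2).
- Tests: 14, Day 15 to Day 2, opened by a significant Week 2 result (Protocol 9.4.2).
- Week 2 planning values: 11% on dupilumab, a 25-point difference (so 36% on abrocitinib), 300 per arm, power at least 99% (Protocol 9.2).

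**Assumptions (not in the documents)**

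- The correlation between daily test statistics is AR(1), with ρ from 0 to 0.95.
- The null days are the earliest k study days.
- Days with a true effect have a mean z of 7, close to the Week 2 planning value in step 1.
- Day 15 stands in for the Week 2 gate, because the Week 2 window in SAP Appendix 2 targets Day 15.

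**Step 1: does the Week 2 gate protect the earlier days?** The standard error is √(0.36×0.64/300 + 0.11×0.89/300) = √(0.000768 + 0.000326) = 0.0331. The expected z is 0.25/0.0331 = 7.56, so power exceeds 99.99%. This agrees with the stated figure of at least 99%. Under the planning assumptions the gate almost always opens and gives null early days almost no protection.

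**Step 2: stop at the first failure.** A false claim requires the first null day in the sequence to reach p<0.05, so the error is at most 5%. Simulation with 400,000 runs per setting gave 4.9–5.1% throughout. The plan's 5% reproduces on this reading.

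**Step 3: the literal sentence.** Once the gate is open, every day with p<0.05 counts. With independent days the error is 1 − 0.95^k:

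- k = 2: 1 − 0.9025 = 9.8%
- k = 3: 1 − 0.8574 = 14.3%
- k = 7: 1 − 0.6983 = 30.2%

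With correlated days, by simulation under the same set-up:

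| Null days k | ρ = 0 | ρ = 0.5 | ρ = 0.8 | ρ = 0.9 | ρ = 0.95 |
|---|---|---|---|---|---|
| 1 | 5% | 5% | 5% | 5% | 5% |
| 2 | 9.7% | 9.1% | 7.8% | 7.1% | 6.4% |
| 3 | 14.3% | 12.9% | 10.3% | 8.8% | 7.6% |
| 7 | 30.2% | 26.6% | 19.3% | 14.8% | 11.6% |
| All 14 | 5% | 5% | 5% | 5% | 5% |

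With all 14 days null, the gate itself holds the error at 5%. Inflation therefore arises only when the gate is a true effect and two or more of the earlier days are null.

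**The case against.** The strongest reply is that the literal reading cannot be what the authors meant. The family is described as sequential and step-down, and the days are put in a fixed order. If every nominally significant day counted, the order would have no effect and the protection statement would be false. In a procedure run in order, the last significant day is naturally the last step passed, meaning the end of the unbroken run. On that reading the sentence does exclude later nominally significant days, and the error is 5%. The same section also spells out a stop-at-first-failure rule.

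Most of this stands. A reader might infer from the sentence that testing never stops, or that the claimed protection is simply not delivered. The documents do not support that stronger reading: the surrounding text points to stopping at the first failure, and then the protection holds.

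The reply does not settle which rule applies. The explicit stop rule is written for the primary and key secondary sequence. The daily tests are set up as an additional family, opened by Week 2 alone and given a different sentence of their own. An analyst could reasonably apply that specific sentence, and the SAP repeats it without clarification.

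Two limits on importance also stand. The inflation figures depend on a correlation and a number of null days that the documents do not give. Onset of itch relief also has its own time-to-event analysis in SAP 6.2.2.3, which does not use this sentence.

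**Conclusion.** This is an ambiguous decision rule, not a demonstrated loss of error control. The sentence is empty as written, appears in both documents, and should be replaced because SAP 5.1 is what permits significance claims for these days.

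The size is conditional. It applies only if the literal wording is followed, Week 2 truly differs, and two or more of the earlier days are null. The familywise error is then about 8–14% for 3 null days and about 12–30% for 7, as ρ falls from 0.95 to 0. Daily itch scores from the same participants are likely to be strongly correlated, so the lower part of each range is more plausible. The primary and key secondary tests are not touched on either reading.

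**What to change.** Before unblinding, replace the stopping sentence in Protocol 9.4.2 and SAP 5.1 with:

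> Testing stops at the first day in this order whose comparison is not significant at the 5% level; neither that day nor any earlier study day will be declared statistically significant.

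This delivers the stated 5% and changes neither the alpha, the sample size nor the power of the primary and key secondary tests. Doing it before unblinding avoids a later choice between two readings that could move the claimed onset day. The cost is one sentence in each document, and the loss of any isolated early-day claim that the literal wording would have allowed.
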